6.3.2 Primary Endpoint: Unified Multiple System Atrophy Rating Scale (UMSARS)

6.3.2.1 Main Analyses

The UMSARS is a clinician-rated scale comprised of four parts. Part I, Historical Review, is an assessment of functioning across various areas. Part II is a Motor Examination. Part III is an Autonomic Examination, and includes supine and standing vital signs, orthostatic change (derived by subtracting standing measurements from corresponding supine measurements), and orthostatic symptoms. Part IV is a Global Disability Scale. Although the UMSARS will be used to collect data in this study, the primary outcome variable for the study will be a modified UMSARS, composed of a subset of items from UMSARS Part I and Part II, with the items selected based on feedback from Health Authorities, expert opinion, and analysis of data from previous clinical trials in MSA.

The UMSARS is assessed during the Screening phase to determine eligibility for study entry and will subsequently be administered at Baseline, and Weeks 4, 12, 24, 36 and 48, Baseline-Extension, Week 12-Extension, Week 24-Extension, Week 36-Extension, Week 48-Extension, and/or early discontinuation.

The primary endpoint is the change from baseline in the modified UMSARS score measured at the Week 48 visit. The items in the modified UMSARS will contain the following Part I items: Speech, Cutting Food and Handling Utensils, Dressing, Hygiene, Walking and Urinary Function. The following Part II items will also be included: Arising from Chair, Posture and Gait. In the analysis of all items, the response categories of 0 and 1 will be combined into a single category of 0 and then subsequent scores recoded to from 2 to 1, 3 to 2 and 4 to 3, reducing the range of scoring options to 0 to 3, before summing the individual items to derive the modified UMSARS.

Summary of primary estimand:

- a. The population of interest for the primary estimand are subjects diagnosed with possible or probable MSA as well as meeting the other inclusion/exclusion criteria of the protocol.
- b. Efficacy is measured by the change from baseline to 48 weeks for the modified UMSARS endpoint.
- c. The treatment evaluated is the treatment as assigned to study subjects. Hence all types of intercurrent events are incorporated using a treatment policy strategy, which evaluates the treatment as assigned and taken including missed or modified doses, drug discontinuation,

and concurrent treatments. Study dropout including dropouts and missed visits due to COVID-19 pandemic (and corresponding discontinuation of assessments) will be handled by a hypothetical strategy to estimate what the outcome would have been at the designated time point if all subjects were continued to be assessed.

d. The mean change from baseline between treatment and placebo on the primary endpoint will be compared at 48 weeks. A significant difference with an error rate of 5% will be required for success.

The summary will be computed using a Mixed Model for Repeated Measures (MMRM) that will include fixed effect factors for treatment group, randomization strata (i.e., disease subtype, diagnostic category, and country), visit, and the treatment group by visit interaction. Baseline modified UMSARS score and the baseline neurofilament level will enter the model as covariates, and subject will be a random effect. Repeated measurements are made on each subject. The covariance structure for within subject error ("R" matrix in SAS proc mixed) will be initially specified as unstructured. If the model fails to converge, then a Huynh-Feldt structure may be used, followed by an AR(1) structure. Error degrees of freedom will be calculated using Kenward-Roger approximation if an unstructured covariance structure fits appropriately; otherwise, a sandwich estimator will be utilized to estimate the covariance structure and degrees of freedom will be calculated using the between-within method.

MMRM-based estimates (i.e., least-squares mean [LSM] with corresponding SD and 95% CI) of values and changes from baseline will be presented by treatment group and week. In addition, the LSM difference in change from baseline between treatment groups (Verdiperstat – placebo) at Week 48 with corresponding SD, 95% CI, and p-value from MMRM will be presented.

Observed values and changes from baseline in the modified UMSARS score will be summarized using descriptive statistics over time by treatment group.

Effect sizes (Cohen's D) of the individual items within the modified UMSARS will also be summarized to assess the strength of the effect of Verdiperstat on each individual item.

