9.4.5 Adjustment for Multiplicity

Type-1 error will be controlled for the primary and key secondary efficacy endpoints by testing them with a gate-keeping procedure. The primary endpoint will be tested at a two-sided alpha level of 0.05. If this test is significant, then the key secondary efficacy endpoints will be tested using Hochberg's procedure. If the test of the primary endpoint is not significant, then the unadjusted p-values for the key secondary endpoints will be presented only for descriptive purposes.

No attempt will be made to adjust for multiplicity when testing the non-key secondary or CCI endpoints. Any endpoints subjected to significance testing are evaluated at an unadjusted two-sided alpha level of 0.05.

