2 STUDY DESCRIPTION

2.1 Study Design

Verdiperstat is a Phase 3, multicenter, randomized, double-blind, 2-arm placebo-controlled parallel-group study designed to evaluate the efficacy and safety of Verdiperstat in a population of patients with MSA (MSA-C and MSA-P). The study is planned to consist of a Screening phase lasting a maximum of approximately 6 weeks and a randomized double-blind treatment phase of approximately 48 weeks, per Figure 1. It is anticipated that the Randomization phase will include a dose titration period of approximately 2 weeks followed by a full dose period of approximately 46 weeks. Approximately 325 subjects in total are planned to be randomized in a 1:1 ratio to receive either Verdiperstat 600 mg BID, or matching placebo BID. It is anticipated that subjects will be assessed at clinic visits, per the Schedule of Assessments & Events (Appendix I: Schedule of Assessments and Events – Randomized Double-blind Phase). In addition, subjects who are completing or have completed Week 48 of the double-blind treatment phase may be offered the opportunity to enroll in an OLE phase, in which subjects will receive open-label treatment with Verdiperstat for approximately 48 weeks (Appendix II: Schedule of Assessments and Events – Open-Label Extension Phase).

Figure 1: Study Schematic

Screening Phase

The purpose of the Screening phase is to ensure that the appropriate subjects are entered into the trial and remain stable during the pre-treatment period. It is estimated that approximately 360 subjects will enter the Screening phase of the trial. The Investigator will determine that the subject meets eligibility criteria and will collect demographic and medical data presenting a full characterization of the subject. All attempts should be made to obtain medical and pharmacy records to confirm the subject's medical and medication treatment history. During Screening,

Biohaven (or designee) may review relevant clinical information to confirm the diagnosis and subtype of MSA, for study eligibility and stratification prior to randomization. Screening will range from a minimum of 1 day to a maximum of 42 days.

If initial Screening lab sample results do not meet protocol-specified eligibility criteria and the Investigator determines that a repeat sample may meet the range required for eligibility, a repeat lab sample may be collected (one repeat collection/analysis allowed).

Rescreening

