5 SAMPLE SIZE, POWER, AND TYPE I ERROR

5.1 Sample Size and Power

The sample size for this study will be approximately 325 randomized subjects.

Based on unpublished data from the Promesa (2016) study.² studying EGCG (epigallocatechingallate) vs placebo with a treatment duration of 48 weeks, the placebo group had a 4.88 point increase with a standard deviation of 4.85 in the modified UMSARS Part I and Part II total score. With an expected improvement of 40% at Week 48 for Verdiperstat compared to placebo, a total of 260 subjects (130 per group) provides 90% power based on a 2-sample, two-sided t-test. With a drop-out rate of ~20%, the study will randomize approximately 325 subjects.

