6.1.4 Adjustments for Covariates and Stratification

The randomization was stratified by disease subtype (MSA-P vs. MSA-C), diagnostic category (possible MSA vs. probable MSA), and country. Hence, treatment group comparisons of continuous efficacy endpoints will be adjusted by disease subtype, diagnostic category, and country. If there are sparse data within a stratum, then stratum may be combined.

The analysis of the primary endpoint and other continuous efficacy endpoints will also be adjusted by the baseline value of the endpoint as a covariate in statistical models.

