6.3 Efficacy

Unless otherwise noted, the primary and secondary efficacy analyses will be conducted on the mITT population. All efficacy data will be included in listings by subject, treatment group, and visit (as applicable). When applicable, the efficacy analyses will be presented for the double-blind and OLE phases, separately and combined. For the OLE phase, no inferential statistics will be derived.

For the double-blind phase, baseline is considered as the last available assessment on or before the first day of study treatment. For the OLE Phase, baseline is considered as (1) the double-blind Week 48 visit assessment for subjects who have been off of the study drug for less than or equal to 4 weeks, or (2) the OLE Baseline-Extension visit assessment for subjects who have been off of the study drug for greater than 4 weeks.

Table 4: Primary, Secondary, and COL Efficacy Estimands and Analyses

Index	Description	Variable Type	Treatment Group Comparison	On-Study Data
Prima	ry Estimand			
P01	Difference between treatment groups in change from baseline in the modified UMSARS scores at Week 48 of the DB Phase	Continuous	MMRM	Screening, Baseline, Weeks 4, 12, 24, 36, 48,
Second	lary Estimand			
S01	Difference between treatment groups in change from baseline in CGI-I score at Week 48 of the DB Phase	Continuous	MMRM	Weeks 4, 12, 24, 36, 48
S02	Difference between treatment groups in change from baseline in MSA-QoL motor subscales score at Week 48 of the DB Phase	Continuous	MMRM	Baseline, Weeks 24, 48, Baseline Ext, Weeks 12 Ext, 24 Ext, 36 Ext, 48 Ext
S03	Difference between treatment groups in change from baseline in MSA-QoL non-motor subscales score at Week 48 of the DB Phase	Continuous	MMRM	Baseline, Weeks 24, 48, Baseline Ext, Weeks 12 Ext, 24 Ext, 36 Ext, 48 Ext
S04	Difference between treatment groups in change from baseline in UMSARS Part I and II total score at Week 48 of the DB Phase	Continuous	MMRM	Screening, Baseline, Weeks 4, 12, 24, 36, 48, Baseline Ext, Weeks 12 Ext, 24 Ext, 36 Ext, 48 Ext
S05	Difference between treatment groups in change from baseline in PGI-S score at Week 48 of the DB Phase	Continuous	MMRM	Baseline, Weeks 4, 12, 24, 36, 48
S06	Difference between treatment groups in change from baseline in CGI-S score at Week 48 of the DB Phase	Continuous	MMRM	Baseline, Weeks 4, 12, 24, 36, 48

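### A second pre-randomization UMSARS score (Screening) is collected but left out of the primary model; adding it is an optional, modest precision gain, not a correction of an error

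*SAP*

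**What the plan says.** SAP 6.3.2.1, on timing: "The UMSARS is assessed during the Screening phase to determine eligibility for study entry and will subsequently be administered at Baseline". The schedules of assessments (Protocol Table 1, SAP Appendix I) show Parts I to IV at both visits. Screening lasts 1 to 42 days (Protocol 4.3.2). Protocol 4.3.1 requires both visits to be face to face, so the Part II items, which may not be rated remotely, are available at each. SAP Table 4 lists Screening among the data for the primary estimand.

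SAP 6.1.4 says the analysis of the primary endpoint "will also be adjusted by the baseline value of the endpoint as a covariate in statistical models". SAP 6.3 defines that value: "baseline is considered as the last available assessment on or before the first day of study treatment". Screening therefore counts only when the Baseline rating is missing. The model in SAP 6.3.1 and 6.3.2.1 has treatment, visit, their interaction, disease subtype, diagnostic category, country, Baseline modified UMSARS and baseline neurofilament. It has no baseline-by-visit term. The imputation model in 6.3.2.3 does have one, but it too uses only the Baseline score, as does the ANCOVA run on the imputed data. No reason is given for leaving Screening out.

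**The concern.** The outcome is change from a single clinician rating, so the error in that rating enters every change score. Adjusting for the same noisy rating removes part of that error. A second pre-dose rating locates the starting level better and can remove more. Because eligibility depends on the Screening UMSARS, the score should exist for nearly every randomized subject.

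At stake is some precision for the primary endpoint, whose test gates all four key secondary endpoints, and for the UMSARS Part I and II total (S04). The validity of the planned analysis is not in question.

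**Working it through.** **1. The plan's own figure.** Protocol 9.4.5 sets the level: "The primary endpoint will be tested at a two-sided alpha level of 0.05". SAP 5.1 takes its variability from an earlier trial in which "the placebo group had a 4.88 point increase with a standard deviation of 4.85". The size it arrives at is stated as follows: "a total of 260 subjects (130 per group) provides 90% power based on a 2-sample, two-sided t-test". The assumed effect behind that size is a 40% smaller worsening than on placebo. SAP 2.1 has subjects "planned to be randomized in a 1:1 ratio to receive either Verdiperstat 600 mg BID, or matching placebo BID".

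- Difference: 0.40 × 4.88 = 1.952.
- n per arm = 2(1.960 + 1.282)² × 4.85² / 1.952² = 129.7, so 130.
- Power at 130 per arm: 90.1% (normal approximation), 89.8% (exact noncentral t).
- 260 / 0.80 = 325 randomized.

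The plan's figures reproduce. They rest on an unadjusted t-test, so no choice of covariate alters them.

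**2. Model for the gain.** None of the following inputs is in the documents except 4.85 and the 1 to 42 day gap.

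- True level at Baseline has variance vT; rating error has variance ve at each visit; reliability = vT/(vT + ve).
- True change over 48 weeks has variance vS, fixed by vS + 2ve = 4.85² = 23.5225.
- The covariance of level and slope is c, and g = gap in days / 336.
- Var(B) = vT + ve; Var(Scr) = vT + g²vS − 2gc + ve; Cov(B, Scr) = vT − gc.
- Cov(change, B) = c − ve; Cov(change, Scr) = c − g·vS.
- V1 (Baseline only) = 23.5225 − Cov(change, B)² / Var(B).
- V2 (both scores) = V1 − Cov(change, Scr | B)² / Var(Scr | B).

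**3. Worked case: baseline SD 5, reliability 0.85, gap 21 days, c = 0.**

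- vT = 21.25; ve = 3.75; vS = 16.0225; g = 0.0625.
- V1 = 23.5225 − 3.75²/25 = 22.96.
- Cov(change, Scr | B) = −0.0625 × 16.0225 + 21.25 × 3.75/25 = −1.0014 + 3.1875 = 2.186.
- Var(Scr | B) = 25.0626 − 21.25²/25 = 7.000.
- V2 = 22.96 − 2.186²/7.000 = 22.28; ratio 0.970, a 3% fall.
- Power 90.7% to 91.5% (normal approximation).

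The two terms in the conditional covariance have opposite signs. The positive one is the measurement-error benefit. The negative one arises because, given Baseline, a lower Screening score also signals faster pre-dose worsening. At SD 5, reliability 0.90, 42 days and c = 0 they cancel: −0.125 × 18.5225 + 22.5 × 2.5/25 = −0.065, and the ratio is 1.000.

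**4. Effect of the gap** (SD 4.5, c = 0): fall in residual variance.

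| Gap | Reliability 0.85 | Reliability 0.90 |
|---|---|---|
| 0 days | 5.1% | 3.7% |
| 14 days | 2.6% | 1.1% |
| 28 days | 1.0% | 0.0% |
| 42 days | 0.1% | 0.4% (Screening coefficient negative) |

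With level-slope correlation 0.3, the 14-day figures are 5.4% and 3.0%.

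**5. Range.** The grid took SD 3.5 to 6 in steps of 0.5, reliability 0.80, 0.85, 0.90 and 0.95, gap 1, 21 and 42 days, and correlation 0 or 0.3 (144 cells). The ratio runs from 0.85 to 1.00, with median 0.97. The power gain at 130 per arm has median 0.8 points and is at most 1.5 points in about seven cells in ten. The largest gain is 3.9 points, at SD 6, reliability 0.80, a 1-day gap and correlation 0.3.

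**6. Simulation check.** ANCOVA, 130 per arm, 4,000 runs, SD 5, reliability 0.85, 21-day gap, with a crude eligibility cut on Screening. The SE falls from 0.594 to 0.587 and power rises from 89.6% to 90.6%. Type I error is 5.2% without Screening and 5.0% with it.

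**The case against.** The strongest reply is that nothing here is wrong: change from baseline with a baseline covariate is a standard analysis, and the gain cannot be sized from the documents. That stands, and it limits the point to an option.

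A reader might infer that the Screening score is guaranteed, free precision worth 10 to 14 extra completers (260/0.963 − 260 = 10; 260/0.949 − 260 = 14). The documents do not support that. Those figures need a zero-day gap, with the two ratings treated as replicates of one unchanged score, whereas the plan allows up to 42 days in a progressive disease. A reader might also infer that Baseline UMSARS is the only adjustment; neurofilament and three strata are in the model too, and the calculation above leaves them out.

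Other points could shrink the gain:

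- Protocol 6.2.3 asks for the same rater throughout where possible. Rating error shared between the two visits reduces what the second rating adds.
- Protocol 5.3 and 5.4 allow washout of restricted drugs during Screening, so for some subjects the Screening score reflects a different treatment state.
- Gaps vary between subjects, so one common coefficient can average opposing effects.
- The formulas assume Week 48-specific coefficients. The main model has no such term even for Baseline, so the change is more than one added coefficient.
- Rescreening may repeat only some procedures, so the SAP must say which score counts.

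These points call for short rules and a lower expectation. None shows bias or harm beyond a few degrees of freedom.

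**Conclusion.** The point holds as a low-priority efficiency suggestion. Two pre-dose scores exist, the model uses one, and the other is a legitimate pre-randomization covariate that leaves the outcome, estimand and error rate as they are. Under the assumptions in step 5, the Week 48 residual variance falls by 0% to 15%, median about 3%, typically 0 to 1.5 power points. A long gap can remove the gain entirely. Baseline SD, reliability and the level-slope correlation are assumptions throughout; blinded data could supply the baseline SD and the Screening-to-Baseline correlation before a decision.

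This should not be read as an error in the SAP, nor as evidence that the trial is underpowered. The stated 260 completers and 325 randomized reproduce and are unaffected.

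**What to change.** Before unblinding, if the sponsor chooses to take the gain:

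- In SAP 6.3.1 and 6.3.2.1, add the Screening modified UMSARS as a covariate. Enter both Baseline and Screening with visit interactions, and keep change from Baseline as the outcome.
- For S04, do the same with the Screening Part I and II total (without item 11).
- After rescreening, use the Screening score closest before Baseline.
- Where Screening cannot be scored, or already serves as Baseline, set it equal to Baseline so that no subject is lost.
- Make the imputation and ANCOVA models in 6.3.2.3 match.

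The cost is SAP wording and programming. Over the five post-baseline visits the model goes from one UMSARS coefficient to ten (five for Baseline, five for Screening), nine more than now. No new data and no further subjects are needed.

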5.2 Type I Error

Type-1 error will be controlled for the primary and key secondary efficacy endpoints by testing them with a gate-keeping procedure. The primary endpoint, the change from baseline in the modified UMSARS score measured at the Week 48 visit, will be tested at a 2-sided alpha level of 0.05. If this test is significant, then the key secondary efficacy endpoints of change from baseline in CGI-I, MSA-QoL motor subscale and non-motor subscale scores, and UMSARS Part I and Part II total score at week 48 will be tested using Hochberg's procedure in which the p-values from the test of each secondary endpoint will be ranked from lowest to highest, and all tests for the null hypothesis of each secondary endpoint with a p-value less than the test with the highest p-value below its critical p-value (defined as 0.05/(k-j+1) where j is the rank of the test and k is the total number of tests) can be rejected.

If the test of the primary endpoint is not significant, then the unadjusted p-values for the key secondary endpoints will be presented only for descriptive purposes, and no conclusions will be drawn from these results.

No attempt will be made to adjust for multiplicity when testing the non-key secondary or endpoints. Any endpoints subjected to significance testing are evaluated at an unadjusted two-sided alpha level of 0.05.

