6.3.1 Continuous Efficacy Endpoints

Measurements are slotted into analysis visits as described in Section 7.2.

Descriptive Analyses

Summary statistics for parameter values are tabulated at select time points by treatment group during the DB and OLE phases, separately.

Treatment Group Comparison Using MMRM

Treatment groups are compared and assessed using MMRM with the following variables:

- Dependent variable, e.g., modified UMSARS score
- Fixed effects (categorical variables): treatment group, visit, treatment group-by-visit interaction, randomization strata (i.e., disease subtype, diagnostic category, and country). Visit represents on-study analysis visit.
- Covariate (continuous variable): baseline value of dependent variable, baseline neurofilament level
- Random effect: subject

Error degrees of freedom are determined by the Kenward-Roger approximation.

The covariance structure for within subject error will be initially modeled using the unstructured covariance matrix. If the model fails to converge, then a Huynh-Feldt structure will be used, followed by an AR(1) structure.

The following statistics are tabulated from the MMRM at select analysis visits:

- Least-squares mean with standard error (SE) and 95% CI by treatment group
- Difference in least-squares means between treatment groups (Verdiperstat placebo) with df, SE, 95% CI, and p-value.

Treatment Group Comparison Using ANOVA

Treatment groups are compared and assessed using ANOVA with the following variables:

- Dependent variable, e.g., brain volume
- Fixed effects (categorical variables): treatment group, baseline value of the dependent variable, randomization strata (i.e., disease subtype, diagnostic category, and country)

The following statistics are tabulated from the ANOVA results:

- Least-squares mean with standard error (SE) and 95% CI by treatment group
- Difference in least-squares means between treatment groups (Verdiperstat placebo) with df, SE, 95% CI, and p-value.

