For each analysis, the imputed data will consist of 1000 imputed data sets (using a MCMC length of 100). Both the parameter-estimation model and the imputation model will include fixed effect factors for treatment group, visit, and the treatment group by visit interaction. The baseline modified UMSARS score and visit by baseline interaction terms will be entered as covariates.

For each imputed dataset, the change from baseline for the modified UMSARS score at Week 48 will be based on observed and imputed data. An ANCOVA model will be used with baseline

modified UMSARS score and randomization strata (i.e., disease subtype, diagnostic category, and country) as covariates, and treatment groups will be compared at Week 48 based on LSM difference between Verdiperstat and placebo in each of the imputed data sets. Results from the analysis of each imputed dataset (LSM treatment differences and standard errors [SE]), will be combined using Rubin's imputation rules to produce a pooled LSM estimate of treatment difference, 95% CI, and a pooled p-value for the test of null hypothesis of no treatment effect.

An additional sensitivity analysis will be conducted on the primary endpoint using the same main analysis described in Section 6.3.2.1 but with a narrower visit window for Week 48 (See Section 7.2).

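### The primary MMRM gives each covariate one common effect from Week 4 to Week 48; if those effects grow with time, part and possibly most of the precision gain at Week 48 is lost, and the imputation models use a different covariate structure

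*SAP*

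**What the plan says.** The primary model in SAP 6.3.2.1 has "fixed effect factors for treatment group, randomization strata (i.e., disease subtype, diagnostic category, and country), visit, and the treatment group by visit interaction". The general MMRM template in SAP 6.3.1 adds "Covariate (continuous variable): baseline value of dependent variable, baseline neurofilament level". Protocol 9.4.2 has the same structure without neurofilament. No baseline-by-visit, neurofilament-by-visit or stratum-by-visit term appears in any of these places. The within-subject covariance is unstructured at first, and the primary endpoint has five post-baseline visits (Weeks 4, 12, 24, 36, 48).

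The key secondary endpoints inherit this form (SAP 6.3.3.1 to 6.3.3.4). CGI-I uses baseline CGI-S as its covariate. The two MSA-QoL subscales are measured only at Weeks 24 and 48 after baseline.

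The multiple-imputation section, SAP 6.3.2.3, is built differently: "Both the parameter-estimation model and the imputation model will include fixed effect factors for treatment group, visit, and the treatment group by visit interaction". It continues: "The baseline modified UMSARS score and visit by baseline interaction terms will be entered as covariates". No strata and no neurofilament are listed there. The ANCOVA fitted after imputation has baseline score and the strata, but not neurofilament.

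**The concern.** The outcome is a change score in a progressive disease. A baseline variable that predicts the rate of decline would plausibly have little effect on the Week 4 change and its full effect at Week 48. One coefficient must then serve all five visits. With an unstructured covariance the fit weights the visits by their precision, and in a progressive disease the early visits are likely to be the less variable ones. The coefficient can therefore be too small for Week 48, the visit that decides the trial, and some of the precision that covariate adjustment could buy is not collected.

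The second issue needs no assumption about growth. The multiple-imputation analyses exist to test the missing-at-random assumption of the primary MMRM. As written, the two analyses differ in the missing-data assumption, in the covariate list and in the shape of the baseline effect. A gap between their results could not be put down to the missing-data assumption alone.

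**Working it through.** **1. The plan's own figure.** Inputs from SAP 5.1 and 5.2: "the placebo group had a 4.88 point increase with a standard deviation of 4.85"; "With an expected improvement of 40% at Week 48 for Verdiperstat compared to placebo"; the primary endpoint "will be tested at a 2-sided alpha level of 0.05".
- Effect: 0.40 × 4.88 = 1.952 points.
- Normal approximation: n per arm = 2 × (1.960 + 1.282)² × (4.85/1.952)² ≈ 130, giving 90.1% power. The noncentral t gives 89.8% at 130 and reaches 90% at 131.
- Drop-out: 260/(1 − 0.20) = 325.

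The plan's figures reproduce. The calculation is unadjusted ("a total of 260 subjects (130 per group) provides 90% power based on a 2-sample, two-sided t-test") and takes no credit for covariates.

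**2. What the common coefficient estimates.** Let β be the vector of true covariate effects at the five visits and S the residual covariance over visits. In large samples the common coefficient converges to

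b = (1′S⁻¹β) / (1′S⁻¹1).

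With complete data, the Week 48 contrast is adjusted by b instead of β48. The share of the possible variance reduction retained is

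[β48² − (β48 − b)²] / β48² = 1 − (1 − b/β48)².

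More than half is lost only if b/β48 is below 0.29.

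**3. Retained share for an effect growing linearly from zero.** The effects, as fractions of Week 48, are 4/48, 12/48, 24/48, 36/48 and 1. Every covariance below is an assumption.

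| Assumed residual covariance | b/β48 | Retained |
|---|---|---|
| Equal variance, independent visits | 0.52 | 77% |
| Random slopes 25% of Week 48 variance | 0.38–0.44 | 61–68% |
| Wiener process plus visit error | 0.27–0.39 | 47–63% |
| Random slopes 50% | 0.25–0.33 | 43–56% |
| Random slopes 75% | 0.12–0.20 | 23–35% |
| Random slopes 90% | 0.05–0.09 | 9–17% |
| Wiener process | 0.08 | 16% |
| SD growing as √time, constant correlation 0.7 | −0.11 | −24% |

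Two rows by hand:
- Equal variance: b/β48 = (0.083 + 0.25 + 0.5 + 0.75 + 1)/5 = 0.517, and 1 − 0.483² = 0.77.
- Wiener: all weight falls on Week 4, so b/β48 = 4/48 = 0.083, and 1 − 0.917² = 0.16.

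In the last row the weights are 1.18, 0.13, −0.07, −0.11 and −0.13, and the common adjustment is worse than none.

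Other growth shapes widen the range. If half the effect is constant over visits, 59–94% is retained. With quadratic growth the share runs from 61% to below zero.

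For MSA-QoL, with two post-baseline visits, linear growth gives b/β48 = (0.5 + 1)/2 = 0.75 under equal independent variances (94% retained) and 0.5 under a Wiener process (75% retained). The loss is smaller there in both settings.

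**4. Check by simulation.** MMRMs were fitted to simulated trials with R-squared 0.10, 200 to 300 runs per setting.

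| Setting | Drop-out | Model SE, common | Model SE, by visit |
|---|---|---|---|
| Slopes 25%, half of the remaining variance shared across visits | none | 0.577 | 0.566 |
| Same | 17% | 0.552 | 0.539 |
| Slopes 75%, independent error | none | 0.585 | 0.565 |
| Same | 16% | 0.561 | 0.542 |

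Drop-out depended on the observed outcome. Without drop-out, b/β48 was 0.39 and 0.20, against 0.38 and 0.20 from the formula. Mean treatment estimates from the two models differed by at most 0.012 points.

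**5. Power at 130 per arm** (noncentral t, variance multiplied by 1 − retained share × R²; R² is assumed):

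| R² | No adjustment | Common, 16% retained | Common, 77% retained | By visit |
|---|---|---|---|---|
| 0.05 | 89.8% | 90.1% | 90.9% | 91.3% |
| 0.10 | 89.8% | 90.3% | 92.0% | 92.6% |
| 0.20 | 89.8% | 90.8% | 94.0% | 95.1% |
| 0.30 | 89.8% | 91.2% | 95.8% | 97.2% |

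Between these two retained shares, the power forgone is about 0.3–1.2 points at R² 0.05, 0.6–2.3 at 0.10 and 1.4–6.0 at 0.30. Power falls below the unadjusted figure only if the retained share is negative: about 88–89.6% at −20% retained, for R² from 0.30 down to 0.05.

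**The case against.** A main-effects MMRM is a valid analysis of a randomized comparison, and the sample size never relied on adjustment. The documents give no covariate-outcome correlation, no visit covariance matrix and no evidence that any baseline effect grows. Baseline measurement error enters the change score at every visit, Week 4 included, so part of the baseline-score effect may well be constant; the common coefficient then retains 59–94%. For one stratum the documents point the other way: Protocol 1.2.1 takes MSA-P and MSA-C to progress at the same rate, and on that premise a subtype-by-visit term recovers nothing. At modest R-squared the gain forgone is a point or two of power.

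All of this stands, and it rules out three stronger readings.
- A reader might infer that most of the adjustment is lost at Week 48. That holds for a near-linear effect when between-subject slope variation exceeds roughly half of the Week 48 variance, or when the SD grows with high correlation. It fails when visit error dominates or part of the effect is constant.
- A reader might infer that every stratum is affected. The premise on subtype argues against that.
- A reader might infer bias, because missing-at-random is conditioned on a misshapen covariate effect. The simulations showed no material difference in the estimates, with or without outcome-dependent drop-out.

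The objection does not answer the inconsistency. The SAP already uses visit-by-baseline terms where it imputes, gives no reason for leaving them out of the primary model, and lists different covariates in the two places.

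**Conclusion.** The point holds as one of efficiency and consistency. The common-effect structure is what the SAP specifies, and under growing effects the pull towards early visits is confirmed by formula and simulation. Its size is uncertain: about 10% to 77% of the Week 48 variance reduction retained for linear growth under most covariances tried, and less than zero in some. The power forgone is roughly 0.6 to 2.3 points at R-squared 0.10. These figures rest on assumed growth shapes, covariances and R-squared values. The retained shares are large-sample, complete-data values, and the simulations cover one R-squared and two covariance settings. The planned 90% power stands without adjustment, and no bias is claimed.

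The mismatch between the primary model and the imputation analyses follows from the text alone. The documents do not show how large its effect on an MMRM-versus-imputation comparison would be.

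**What to change.** In SAP 6.3.1 and 6.3.2.1, add baseline value-by-visit and baseline neurofilament-by-visit terms to the MMRM; for CGI-I (SAP 6.3.3.1), use baseline CGI-S-by-visit. Diagnostic category-by-visit is optional. Subtype-by-visit is low priority given the protocol's premise of equal progression. Country stays a main effect.

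In SAP 6.3.2.3, give the imputation models and the post-imputation ANCOVA the same covariates and strata as the primary model. That means adding the strata and neurofilament (with its by-visit term) to the imputation models, and neurofilament to the ANCOVA, which looks at Week 48 only and needs no visit terms. A difference between the MMRM and the imputation results would then reflect the missing-data assumption only.

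The cost is SAP wording, plus four extra coefficients per term with five post-baseline visits (one for MSA-QoL, which has two), against about 325 subjects. If the effects turn out constant over visits, almost nothing is lost.
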